7.3 Reminders

All participants will receive **standard** email reminders for activities, such as password changes and reminders when surveys are available (**Attachment 22**).

7.4 Participant-facing results

Aggregate summary results of the study will be posted on the LUNGeVity website and will be periodically updated as participants join the study and complete more follow-on surveys.

The study is an open-ended longitudinal survey study. Protocol extensions will be submitted as needed throughout the duration of the study.

7.5 Study risks

All participants: Recruitment and participation in the study itself does not put potential study participants at risk.

Self-report participants not from a market research firm, specialty pharmacy, or trial website: There are no privacy concerns associated with recruitment given that all recruitment will be conducted through online means and not use any touch-points with patients or their caregivers.

Self-report participants from a market research firm, specialty pharmacy, or trial website: There is minimal risk for privacy concerns. Since: 1) these participants will be recruited by staff that have completed the appropriate training for the conduct of research and will recruit participants according to this training. 2) The market research firm, specialty pharmacy, and trial website **will not** have access to participants survey responses. 3) LUNGeivity **will not** have access to the market research firm, specialty pharmacy, and trial website network data.

Clinic participants: For patients and caregivers recruited at a clinic site, there is minimal risk for privacy concerns. Since: 1) these participants will be recruited by clinic staff that have completed the appropriate training for the conduct of research and will recruit participants according to this training. 2) The clinic site **will not** have access to participants survey responses. 3) LUNGeivity **will not** have access to the clinic site's patient data.

All study participants will be provided a link that directs them to the study surveys. Responses will be confidential and only analyzed in aggregate, and personally identifiable information will not be shared with outside parties.

As with all electronic data capture systems, there is a potential risk of breach of confidentiality of personal and medical information and the associated privacy of study participants. Such risks will be minimized by (1) storing personal identifiable information (e.g., subject names) in tables separate from other study information; (2) limiting direct access to information contained within the study to trained LUNGeivity and EmpiraMed research personnel; (3) de-identifying any shared data; and (4) the use of a secure, compliant, well-established, and proven software application (PRO Portal).

7.6 Withdrawal or removal from study

Withdrawal: If a study participant wishes to withdraw from the study, they may do so by emailing the Principal Investigator or by accessing the Forms and Privacy Settings section of their personal profile and selecting "withdraw". They can still redeem their earned points for eGifts before their account becomes inactive; redemption of the points that they have accumulated is not contingent upon study completion. Their email address and other identifiable information will be removed from the database and they will no longer be asked to provide additional data to the

study. Data that have already been collected will not be removed from the study. Study participants will be given the option to provide a reason for their withdrawal in the PRO Portal. **(Attachment 12)**

Removal: The Principal Investigator may remove a study participant from the study under the following circumstances:

- LUNGeivity Foundation or IRB cancels the study
- The Principal Investigator thinks that removing a study participant from the study is in their best interests
- A study participant is not responding to the surveys or not following directions given for the study. In this case, an email to the study participant notifying them of their non-compliance will be sent to the registered email address **(Attachment 4)**
- The Principal Investigator suspects fraudulent participation in the study **(Attachment 23)**

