2.0 Study Synopsis

The study objective is to collect longitudinal data to facilitate a more rigorous understanding of the diagnostic and treatment journey of people diagnosed with lung cancer and to identify determinants of treatment heterogeneity. Study data will facilitate a deeper and more scientifically rigorous understanding of the needs and wants of people living with lung cancer and assist with the integration of patient experiences into the development of lung cancer treatments and research. It supports ongoing efforts at the U.S. Food and Drug Administration (FDA) to promote patient-focused drug development (PFDD).¹

During this study, surveys will be deployed to catalog different components of a patient's diagnostic and treatment journey, along with how a lung cancer diagnosis impacts the quality of life of those living with lung cancer. Study participants will consent and register for the study and complete an initial baseline survey. They will then be followed for 12 months and receive a monthly survey (11 surveys in total). The development of the surveys has been guided by input from patients, clinicians, FDA experts, and incorporates questions from existing PRO measures.

Summarized study results will also be posted on LUNGeivity's website. External researchers will be able to apply to LUNGeivity Foundation to administer additional surveys to study participants. They can also apply to have limited access to de-identified data. The study is an open-ended longitudinal survey study. Protocol updates and amendments will be submitted to the IRB throughout the duration of the project as needed.

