4.0 Objectives

The study objective is to collect longitudinal data that facilitates a more rigorous understanding of the treatment experiences and needs of patients with lung cancer—either reported by patients or through their caregivers. This research project will catalog different elements of a patient's diagnostic and treatment journey and identify unmet needs of patients with lung cancer. This is an international study with an open-ended timeframe.

[figure not shown]
The study will collect data to answer the following questions:

1. What are some of the first-line treatment options prescribed to patients?
2. What are the reasons for treatment change and second- and subsequent-line treatment options (including immunotherapy (I/O) and clinical trials)?
3. What types of biomarker testing practices were utilized to diagnose the cancer and characterize mechanisms of resistance?

4. Are there specific risk factors that can predict the histology of the disease and response to specific treatments?
5. How does a lung cancer diagnosis impact the quality of life of a patient?
6. Which symptoms, impacts, and outcomes do patients with lung cancer experience and how do these change over time (collected through validated patient-reported outcome instruments)?
7. Do patients who have participated in clinical trials have better outcomes than those who have not participated in clinical trials?

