6.4 Consent

Study participants will sign up for the study and complete surveys through an online platform (PRO Portal). No pen-and-paper version of the surveys in the study will be used. Participation in the study is completely voluntary, and study participants will be recruited through methods described above. Before commencing the baseline survey, all participants will be instructed to read and sign the study eICF during the registration process. Study participants will have the option to download the signed eICF for their own records. There will be two versions of the eICF – one for United States study participants (**Attachment 5**) and one for non-United States participants (**Attachment 6**). This separation has been done to include GDPR-related information in the eICF for non-United States study participants.

If a study participant withdraws their consent, they will not be contacted further and will not be asked to contribute additional data to the study. They will be given the option to share their reason for withdrawal (**Attachment 12**) If invitations when follow-on monthly surveys bounce back or if LUNGeivity receives notice that the study participant has passed away, LUNGeivity will withdraw the patient. Their existing survey responses will not be removed from the study but any personally identifiable information (PII) will be removed. If a caregiver's patient passes away during the study, the caregiver's participation is complete following the completion of a close-out bereavement survey.

A study FAQ is available for participants once they are registered (**Attachment 13**). Participants will also have access to a Quick Start Guide on the study landing page (**Attachment 14**)

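### Removal for not answering surveys has no threshold or way back; it discards later surveys that question 6 needs and may tilt later months toward healthier participants

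*Combined protocol and SAP*

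**What the plan says.** Section 7.6 opens its list of grounds with "The Principal Investigator may remove a study participant from the study under the following circumstances". One of the grounds is "A study participant is not responding to the surveys or not following directions given for the study". The only step attached to it is a notice: "In this case, an email to the study participant notifying them of their non-compliance will be sent to the registered email address". The section does not say how many missed surveys count, over what period, whether illness is an exception, or whether a removed participant can return. Suspected fraud is treated more fully in Section 7.7, which gives the participant 7 days to answer before being flagged.

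Before any removal, Section 7.3 offers only standard "email reminders for activities, such as password changes and reminders when surveys are available".

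Section 6.4 handles two other exits. If survey invitations bounce, or if "LUNGeivity receives notice that the study participant has passed away, LUNGeivity will withdraw the patient", identifying details are deleted and earlier answers are kept.

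The schedule is a baseline survey and 11 monthly surveys. Question 6 in Section 4.0 asks "Which symptoms, impacts, and outcomes do patients with lung cancer experience and how do these change over time". Section 8.0 names frequencies, cross tabulation, time-series and regression. It says nothing about missed surveys, removals or deaths.

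**The concern.** In lung cancer it is plausible that a participant stops answering because of progression or an admission, and that some of these people would answer again. A longitudinal analysis gains a lot from such returns: they show what happened after the gap and help to correct for it. A removed participant is no longer followed, so those surveys are lost by design and no later analysis can recover them.

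If silence is more common among people who are ill, and the same people tend to stay ill, removal also changes who is left. The later months would then describe a group healthier than the living cohort, and a symptom course read from them could look too favourable.

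**Working it through.** **No stated figure to reproduce.** The documents give enrolment targets (1,200 patients, 300 caregivers) and 12 surveys, but no response rate, dropout rate or power calculation. The sizes below are illustrations under assumed inputs.

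**Assumed inputs.** Each month 8% of the well become ill and 30% of the ill recover, so the share ill settles near 8/(8+30) = 21% before deaths. Of those ill, 4% die each month. The well answer 90% of surveys; the ill answer 45%, or 70% as an alternative. A participant is removed after two or three consecutive misses, or never. There are 11 follow-up surveys and 400,000 simulated patients. The true share ill among the living at the last survey is 20.0% if each month's deaths are applied before the change of health state, and 19.3% if after; hence the ranges.

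**Step 1: no removal.** With true share p, the share ill among responders is

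p × r_ill / [p × r_ill + (1 − p) × r_well].

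With p = 0.20, r_ill = 0.45 and r_well = 0.90, this is 0.09 / (0.09 + 0.72) = 11.1%, which matches the simulation. This shortfall exists without any removal rule.

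**Step 2: add removal.**

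| Ill answer | True share ill | No removal | After three misses | After two misses |
|---|---|---|---|---|
| 45% | 19.3-20.0% | 10.6-11.1% | 9.8-10.3% | 8.7-9.1% |
| 70% | 19.3% | 15.6% | 15.4% | 14.7% |

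**Step 3: split the shortfall.**
- Ill answer 45%, true 19.3%: non-response alone costs 19.3 − 10.6 = 8.7 points. Removal adds 10.6 − 9.8 = 0.8 points (three misses) or 10.6 − 8.7 = 1.9 points (two). Non-response therefore accounts for 8.7/9.5 = 92% or 8.7/10.6 = 82% of the total.
- Ill answer 70%, true 19.3%: non-response alone costs 19.3 − 15.6 = 3.7 points. Removal adds 0.2 or 0.9 points.

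**Step 4: lost data.** If the ill answer 45%, two-miss removal takes out about 32% of living participants and loses about 13% of the responses otherwise obtainable. If the ill and the well both answer 90%, it still loses about 4%.

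**Step 5: when the added bias disappears.**
- Response unrelated to health (90% in both states): no bias, only lost data.
- Brief illness: doubling onset and recovery to 16% and 60% a month keeps the settled share at 16/76 = 21%. With the ill answering 45%, responders show 11.2% ill with no removal, 11.2% after three misses and 10.9% after two.

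**Step 6: a second model.** Here each person has a symptom score, the top 25% in a month count as ill, and response is 90% when well and 50% when ill.

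| Share of variance that is stable within a person | No removal | After three misses | After two misses |
|---|---|---|---|
| 0 | 15.6% | 15.7% | 15.7% |
| 0.3 | 15.6% | 14.7% | 12.8% |
| 0.6 | 15.6% | 13.3% | 10.0% |
| 0.8 | 15.6% | 12.0% | 7.6% |

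Persistence drives the added bias. Even in the worst row the added part (15.6 − 7.6 = 8.0 points) stays below the part due to non-response (25 − 15.6 = 9.4 points).

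**The case against.** The strongest reply is that the clause is permissive. The Principal Investigator may remove, a notice goes out, and nothing obliges removal after one or two gaps. Section 7.1 points the same way: the consequence it states for 60 idle days on the portal is the loss of 100 hearts. An automatic one-miss rule, which in the first model would remove about 84% of living participants, is not a credible reading. Most of the distortion at two or three misses comes from non-response and would remain if the clause were deleted.

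All of this stands, and it limits the size of the point. It does not remove the point. Discretion without a threshold means that two participants with the same gap can be treated differently, and the analyst has no rule to model. Nothing in Section 8.0 compensates.

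Two stronger readings are tempting and are not supported:
- A reader might infer that short gaps become permanent losses. The text does not say that removal follows a short gap or that it is irreversible; permanence is only an inference from the absence of a return route.
- A reader might infer from Section 6.4 that death, lost contact and refusal cannot be told apart, because both bounced addresses and deaths lead to withdrawal by the sponsor. The text does not say how the reason for exit is recorded. Participants who withdraw are offered a reasons form (Attachment 12), which is not among the text available here. All that can be said is that the protocol body specifies no separate, dated exit codes.

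**Conclusion.** The point holds in a limited form. Non-response is a stated, undefined ground for removal, and using it discards return surveys that question 6 needs. Under the assumed rates, two-miss removal costs about 4% to 13% of obtainable responses.

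A shift toward healthier participants is a possible further harm, not an established one. It requires that silence is linked to health and that illness persists. In the first model, removal then adds about 0.2 to 0.8 points after three misses and about 0.9 to 2.0 points after two, on top of 3.7 to 8.9 points from non-response itself. The second model allows a larger addition when symptoms are very stable within a person, and almost none when they are not. The documents supply neither the response rates nor the degree of persistence, so these are illustrations and not estimates for this study. The statement that the clause will make later months look healthier goes further than the documents allow.

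The clause is still worth changing, because the change is cheap and the lost surveys cannot be recovered later.

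**What to change.** - In Section 7.6, delete non-response as a ground for removal, and state that a missed survey alone does not count as failing to follow study directions. Keep sending the scheduled invitations through survey 12.
- Leave the other exits as they are: consent withdrawal, death, bounced address, the participant's best interests, suspected fraud and study cancellation.
- Record the reason and date of every exit under separate codes: consent withdrawn, death, email bounced, removed (with the ground).
- In Section 8.0, state that the analysis for question 6 treats missed surveys as intermittent missing data and uses every survey returned, including those after a gap. This does not cure the bias from non-response itself, so the results should carry that caution.

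The cost is a protocol wording change, a few more automated emails, a little more analysis work and a lower reported completion rate, because silent participants stay in the denominator. Rewards follow completed surveys, so keeping silent participants adds little incentive cost.

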7.7 Detection of possible fraudulent participation

The research team is committed to ensuring the integrity of the data collected, both to respect authentic participants from the lung cancer community and to maintain the rigor and robustness of the data collected. To achieve this, they have taken every precaution to deter fraudulent participation in Project PEER, such as:

- Use of CAPTCHA at the time of participant registration
- Use of a short verification survey **(Attachment 9)** to confirm whether a participant is a person with lung cancer or a caregiver to a person with lung cancer
- Pacing of study participation incentives every 3 months whereby a participant will receive an incentive after completing 3 surveys broken into 4 periods (totally 12 surveys). This is described in detail in Section 7.1

In addition to these precautions, we will flag participants who have registered with duplicate emails and/or duplicate usernames as fraudsters. In the event that a participant is identified to have duplicate accounts, they will receive the fraudulent participant email **(Attachment 23)** and have the opportunity to rectify the misidentification. A participant will be flagged as fraudulent only if they fail to respond to the fraudulent participation email within 7 days of receiving the email. We will also be doing period data quality controls before each incentive is paid out (after completion of survey # 3, 6, 9, and 12):

- Step 1: For all participants, we will be tracking their responses over time and checking for inconsistencies such as **a large selection of “I do not know” for different questions within the same survey and variations in data collected through each monthly survey.** For example, baseline and monthly surveys administered to both patients and caregivers have common questions. Variations, such as fluctuation in treatment-related and patient or caregiver experience data, will be easily identified during data quality control.
- Step 2: For those participants where such variations and/or inconsistencies are identified, we will look at survey para data to identify whether the participants identified in Step 1

finished the survey really quickly – defined as time taken to complete the survey that is two standard deviations lower than the mean completion time. This time limit has been decided based on previously published research.¹³ The PRO portal allows researchers to access survey para data (**mean survey completion time** for all participants and **individual participant completion time** for each survey). It is important to note that different survey para data time limit values will be used for patients and caregivers, given the different lengths of the surveys.

- **Step 3:** In the event that a participant is identified through Step 2, they will receive the fraudulent participant email (**Attachment 23**) and have the opportunity to rectify the misidentification. A participant will be flagged as fraudulent only if they fail to respond to the fraudulent participation email within 7 days of receiving the email.

Given all the precautions we have taken, we do not anticipate many fraudulent participants. In the event that a participant is suspected of being fraudulent, we will deal with each situation on a case-by-case basis based on their survey responses and the survey para data.

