5.0 Study Workflow

A GDPR-compliant workflow for the study is shown below.

Briefly,

1. Potential participants will be directed to the study landing page (**Attachment 1**) through various recruitment methods (section 6.3).

2. They will then fill out the Self Registration Form (**Attachment 2**)
3. They will then be asked to read the Registration Data Use Agreement and complete the Registration Form (**Attachment 3**)
4. Following creation of account on the PRO Portal and system determination the cohort maximums have not been met (either within the 1200 patients or 300 caregivers), an email verification (**Attachment 4**) will be sent to potential participants.
5. After account verification, a potential participant will sign the electronic informed consent form (eICF) (**Attachment 5 and 6**)
6. After a potential participant has consented, they will agree to and sign the Terms of Use Agreement and Privacy Policy (**Attachment 7 and 8**)
7. The potential participant will complete a brief survey (**Attachment 9**) to verify that they are a lung cancer patient or caregiver as a means to screen out “fraudsters”
8. At this stage a potential participant is considered a study participant and is able to commence participation.

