7.0 Study Design and Methods

7.1 Financial Incentives

Study participants will be incentivized minimally to complete all the surveys. It is anticipated that a study participant will receive \$20 (in the form of an eGift card) every 3 months – a total annual incentive amount to not exceed \$80 for a total of 12 surveys (1 baseline and 11 follow-up surveys). Compensation is dependent on successful completion of all surveys sent out by the research team. The schedule of compensation is based on the number of completed surveys. The PRO Portal awards “Hearts” (which are a particular type of points) for completion of monthly surveys, diary entries, and other information study participants may report directly into the system. Hearts are awarded independent of a participant's specific answers to questions. In addition, the number of hearts a study participant receives will vary depending on the scope of the data collected. Hearts can be redeemed for cash gift cards (called eGifts) which are distributed to them via email. Once every three months, 800 hearts can be redeemed for a \$20 eGift that a participant can choose from a selection of popular merchants. Inactivity for 60 days on the PRO Portal will lead to the expiration of 100 hearts. The study-specific rules about accumulation of points and eGift redemption limits can be accessed in the PRO Portal by clicking on the Rewards tab. If a study participant withdraws from the study early, they can still redeem their earned points for eGifts prior to withdrawal; redemption of the points that they have accumulated is not contingent upon study completion. If a participant is removed from the study

by the Principal Investigator for suspected fraudulent involvement, they will not be able to redeem any pending rewards.

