Patients will also have the option to provide additional information by logging on to their account and providing information in their eDiary. The eDiary will chart a patient's compliance with

medications with food and weight as well as the option of “checking in”. This is completely optional. A screenshot of the eDiary option is included in **Attachments 17A, B, and C**.

The consent process will explicitly discuss the time needed to complete surveys.

Summary of the different PRO instruments to be used in Module 3 for patients is as follows:

1. A PRO-CTCAE side-effect question— Please choose the response below that best describes the severity of your **overall side effects from treatment** over the past week” (where 0 = none and 4 = very severe)
2. SAQ items for **all-comers**, including small cell lung cancer (SCLC) patients to understand how SAQ may be applied to the SCLC population ⁴
3. EORTC short-form questions on physical/functional/emotional functioning, fatigue, and pain^{5,6}
4. EORTC questionnaire on financial toxicity⁷

Caregivers:

Once caregivers provide informed consent, at the beginning of their participation they will be asked if the patient they care for is deceased or still alive.

If during the caregiver’s baseline survey (**Attachment 18**), they report that their patient is deceased, they will be compensated \$20 for their time upon completion of their survey. These caregivers will not receive any follow on monthly surveys.

The **baseline survey (Attachment 18)** for caregivers is modular and contains the following sections:

- **Module 1** will ask caregivers about their role in caregiving.
- **Module 2** will ask caregivers questions about their patient’s lung cancer diagnostic experience
- **Module 3** will include caregiver-specific questions on quality of life and coping mechanisms as a caregiver (including the CarGOQoL instrument^{8,9} and the Enriched Social Support Instrument¹⁰)
- **Module 4** will ask caregivers questions specific to their lung cancer, including questions on biomarker testing and different treatment options
- **Module 5** will ask caregivers about their demographic characteristics

Caregivers whose patients are alive at the time of study initiation and who have completed the baseline survey will also be asked at the start of each follow-on survey if the patient they provide care for is still alive. There will be 11 additional **follow-on surveys** (one every month after a

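### Periodic data-quality controls start at survey 3, so one- and two-survey records get only entry checks, and the $20 for baseline-only caregivers has no such control scheduled

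*Combined protocol and SAP*

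**What the plan says.** Section 7.7 has two layers of protection against false participation.

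- **Entry checks.** These are "Use of CAPTCHA at the time of participant registration", flagging of duplicate emails and usernames, and a short verification survey. Section 5.0 places that survey before participation begins and describes its purpose as "to verify that they are a lung cancer patient or caregiver as a means to screen out" fraudulent registrants. Section 7.7 also counts as a precaution the pacing of incentives, one for every three surveys over four periods.
- **Periodic controls.** These take place "before each incentive is paid out (after completion of survey # 3, 6, 9, and 12". Step 1 reads: "For all participants, we will be tracking their responses over time and checking for inconsistencies such as" many don't-know answers within one survey, and variation between surveys. Step 2 is narrower: "For those participants where such variations and/or inconsistencies are identified, we will look at survey para data", to see whether the survey was finished more than two standard deviations faster than the mean. Step 3 is an email; the participant is flagged only after 7 days without a reply.

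Three other provisions bear on this. Under Section 7.2, a caregiver who reports at baseline that the patient has died receives $20 for that survey, and "These caregivers will not receive any follow on monthly surveys". Under Section 7.6, a withdrawing participant's email address is deleted but the answers stay. Under Sections 7.4 and 8.0, aggregate results are posted and "will be periodically updated as participants join the study and complete more follow-on surveys".

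**The concern.** The periodic controls are the only scheduled step that examines what a participant answered and how fast. They are tied to survey counts, while data become usable, and one payment falls due, before the first count is reached.

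Research Questions 1 and 3 in Section 4.0 (first-line treatment and biomarker testing) draw heavily on Module 4 of the baseline survey. A false baseline followed by silence would therefore count in those tables without its answers or timing having been looked at. Delay can also make the gap permanent: once a withdrawing participant's email address is gone, the Step 3 email cannot be sent.

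**Working it through.** **Reproducing the plan's figures.** Inputs: 1 baseline + 11 follow-up = 12 surveys, and $20 per period (Section 7.1); control points at surveys 3, 6, 9 and 12 (Section 7.7).

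- Maximum incentive: 4 × $20 = $80, as Section 7.1 states.
- Six surveys completed: 2 control points × $20 = $40, as in the Section 7.2 example.

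On the standard schedule, then, each $20 follows a control.

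**Control points reached, by surveys completed.**

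| Surveys completed | Control points reached |
|---|---|
| 1–2 | 0 |
| 3–5 | 1 |
| 6–8 | 2 |
| 9–11 | 3 |
| 12 | 4 |

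Once survey 3 is done, the baseline has come within a scheduled control. The gap is confined to records of one or two surveys. A baseline-only caregiver has one survey, no control point and a $20 payment; this holds for all of that group and needs no assumption.

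**How many records (assumed shares; the documents give none).**

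- If 5–40% of 1,500 participants stop before survey 3: 0.05 × 1,500 = 75 to 0.40 × 1,500 = 600 records.
- If 5–30% of 300 caregivers are baseline-only: 15 to 90 people, paid 15 × $20 = $300 to 90 × $20 = $1,800 in total.

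**Possible effect on a patient baseline proportion.** Preventable shift = (share stopping before survey 3) × (share of those that are false) × (difference in answers) × (share of false records the control would catch). All four inputs are assumptions. Take 10–40% stopping (120 to 480 of 1,200 patients), 10–30% false, a 30-point difference, and a catch share of 1:

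- Low: 0.10 × 0.10 × 30 × 1 = 0.3 points.
- High: 0.40 × 0.30 × 30 × 1 = 3.6 points.
- Yardstick, the 95% sampling half-width at a proportion of 0.5: 1.96 × √(0.25/1,200) = 2.83 points.

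Even at the high corner, the control would have to catch 2.83/3.6 = 79% of the false records for the preventable shift to exceed the half-width. Flagging requires a Step 1 finding, an unusually short completion time and no reply within 7 days, so a catch share of 1 is generous.

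**The case against.** **Entry checks exist.** A reader might infer that early-stopping records are never screened. The documents do not support that. Everyone meets CAPTCHA and the verification survey, and duplicate flagging is not tied to a survey number. The investigator may remove anyone suspected of fraud (Section 7.6), and suspected cases are handled individually (Section 7.7). This stands. But the entry checks do not look at baseline answers or speed, and the discretionary routes need a suspicion that no scheduled review would raise for these records.

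**The schedule sentence speaks of each incentive.** On that reading the $20 to baseline-only caregivers might be covered, and the defect would be one of wording. This is fair as far as it goes. The bracketed survey numbers still give the only timing, and this group cannot reach any of them.

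**Hearts.** Section 7.1 awards hearts for "completion of monthly surveys, diary entries, and other information study participants may report directly into the system", and withdrawers may redeem what they have earned, so a reader might infer that payment can come before survey 3. This is not shown. Redemption takes 800 hearts, once every three months; the hearts earned per activity are not given; and Section 7.1 also ties compensation to completed surveys.

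**Motive.** A reader might infer that early-stopping records are those most likely to be false, made for quick money. For patients this fails: on the stated schedule they earn nothing before survey 3, and early stopping can reflect illness or death.

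**Reach.** Section 8.0 analyses patients and caregivers separately, so baseline-only caregivers cannot distort the patient tables. This stands; they affect the caregiver results only.

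**Conclusion.** The gap is real but limited. As written, no periodic control of answers or completion time is scheduled for a record of one or two surveys, yet the record is retained and can enter baseline tables and posted summaries. The one-survey caregiver payment is an exception to the pacing that Section 7.7 presents as a safeguard.

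The size of any bias cannot be determined from the documents. The range of 0.3 to 3.6 points is an illustration, not an estimate: it assumes perfect detection and exceeds the sampling half-width only near its top. It also presumes that a flagged record is left out of the analysis, which Section 7.7 implies but does not state. The case for changing the plan rests on the scheduling gap and the low cost of closing it, not on a demonstrated bias.

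Separately, the synopsis and Section 6.2 require the patient to be alive, while Section 7.2 admits and pays caregivers of patients already deceased. These passages must be reconciled. Excluding that group would remove the payment exception but leave the one- and two-survey gap.

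**What to change.** 1. Apply the within-survey part of Step 1 (many don't-know answers) to every baseline survey and, for those it identifies, the Step 2 completion-time check. Do this before the survey enters any analysis or posted summary.
2. Do the same before the one-survey caregiver payment and before any redemption at withdrawal, while the email address needed for Step 3 is still held.
3. Keep the between-survey comparison at surveys 3, 6, 9 and 12, since it cannot be made on a single survey.
4. State that flagged records are left out of analyses and summaries, and reconcile the living-patient criterion with Section 7.2.

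No new instrument is needed: the don't-know check already works within one survey, and Section 7.7 says the portal holds individual completion times for each survey. The cost is a little more data-management time and slightly later payment for baseline-only caregivers and early withdrawers. Some genuine participants will also receive the Step 3 email, because Section 7.2 recognises that patients may need their medical records to answer; they can reply and clear themselves. The change will not catch every false record.
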